RESTORE RESILIENCE IN CRITICALLY ILL CHILDREN – R2

Principal Investigators

[name], RN, FAAN
University of Pennsylvania
School of Nursing
[name]
[name]
[contact]
[contact]

[name]
Children's Hospital of Philadelphia
Anesthesiology and Critical Care
[name]
[name]
[contact]
[contact]

[name]
Johns Hopkins University School of Medicine
Charlotte R. Bloomberg Children's Center
[name]
[name]
[contact]
[contact]

Funding Sponsor

National Institute of Child Health and Human Development
National Institute of Health, [name]
[name]

IRB Number

828061

NIH Grant Number

R21-HD093369-01

Initial version

8/17/17

Version 2:

11/3/2017

Version 3:

12/13/2017

Version 4:

1/2/2018

Version 5:

2/12/2020

Version 6:

7/28/2020

Version 7:

9/18/2020

CONFIDENTIAL

Study Summary

Title	RESTORE Resilience in Critically Ill Children – R2
Short Title	R2
IRB Number	828061
Methodology	A prospective cohort study with a convenience sample of patients admitted to the PICU at two study sites.
Study Duration	Study participation will be completed at PICU discharge or PICU Day 28, whichever occurs first.
Study Center(s)	This is two-site study, CHOP & Johns Hopkins.
Objectives	The study design will allow investigators to describe usual care in each PICU and identify the facilitating and restraining factors impacting the implementation of R2 at each PICU. The purpose of this pilot study is to improve the care, environment, daily routine and sleep patterns of children in the PICU. The goal of this study is to learn what can be improved to support a critically ill child’s healing and circadian rhythms.
Number of Subjects	Each site will enroll 10 baseline (control) subjects and 20 intervention subjects.
Main Inclusion and Exclusion Criteria	
Inclusion Criteria: PICU admission at one of the study sites in which elements of R2 are typically but sporadically implemented; Between the ages 6 months and 18 years at the time of enrollment; Intubated and mechanically ventilated within the last 48 hours; acute lung disease is the primary reason for intubation; ≤4 nights in the hospital (≤2 nights in PICU); Parental/Guardian provides primary care for child;
 
Exclusion Criteria: ; child has a baseline cognitive dysfunction ≥4, measured by the Pediatric Cerebral Performance Category (PCPC); Transferred to the PICU from another hospital unit/ward ≥4 days (≥2 nights in the PICU); admitted with an uncontrolled seizure disorder, cerebral hypertension, neuromuscular respiratory failure, ventilator dependence (excluding BiPAP or CPAP at night); history of inability to tolerate bolus;. enteral feeds; the presence of any of the following within 24 hours of admission: modal pain scores > 4; persistent hypotension/hypertension unresponsive to standard therapies; use of High Frequency Oscillatory Ventilation or Extracorporeal Membrane Oxygenation; administered melatonin within the past week or have active do-not-resuscitate plans.

Intervention	During the intervention phase the following will occur: 1) parents will complete the Child’s Daily Routine and Sleep Survey, 2) cycled day-night lighted and modulation of sound will be provided to match the child’s routine (provided by the parent), 3) the subjects sedation will be managed using the RESTORE process that is standard care at both sites, 4) night fasting with bolus enteral daytime feedings will be administered per child’s routine feeding schedule (unless contraindicated), 5) the PICU Up! program will be implemented, 6) the number of nurses assigned to care for the subjects will be limited, and 7) parents will be asked to complete a paper or electronic diary during the child’s PICU stay to track the day’s events, their thoughts, or questions they may have for the care team.

CONFIDENTIAL


Statistical Methodology
	
Descriptive statistics will be calculated, including means, standard deviations, medians, and interquartile ranges for continuous variables and frequency counts and percentages for categorical variables. Data will be examined for skewness, outliers, and systematic missing data. For non-normal continuous outcomes, we will consider data transformations or nonparametric methods, as appropriate. Our primary analysis will compare the circadian activity ratio post-extubation between Baseline Phase and Intervention Phase patients using t-tests or Wilcoxon rank-sum tests, as appropriate. Secondary analyses will use linear regression to control for variables that could be associated with outcomes, such as patient severity or age group. Analysis of secondary outcomes will use t-tests or Wilcoxon rank-sum tests for continuous variables and Fisher's exact tests for categorical variables. Regression methods (linear, logistic, proportional hazards) will be used to assess the effects of covariates on secondary outcomes. Though we do not anticipate differences due to gender, race/ethnicity, or center, we will assess main effects and possible effect modification due to these factors using regression methods. Data analyses will be performed using SAS® or similar statistical packages.

Data and Safety Monitoring Plan
	
This PI and data coordinating site (Children's Hospital Boston) will be responsible for data quality and safety of all subjects.

Background and Study Rationale

This is a research study and will be conducted in full accordance with all applicable University of Pennsylvania Research Policies and Procedures and all applicable Federal and state laws and regulations as applicable.

1 Introduction

Maintaining a child's circadian rhythm during their critical illness may strengthen their resilience and, in the very least, not burden a child's already compromised state. Optimizing CR during critical illness has been shown to be feasible and safe, improve patient-important outcomes, and is therefore now recommended as one of the best practices and priorities among adult ICUs. Although each R2 element is currently practiced in 58 PICUs, the R2 bundle has not been systemically implemented or tested. The first step in a paradigm shift is to ensure there is supporting evidence for the planned change in care. Therefore, a systematic approach is urgently needed to optimize the healing milieu in the PICU and characterize the functional changes that occur as a result of disrupted circadian rhythms in PICU survivors. Our interprofessional team believes that PICU care and environments can be modulated to sustain a child's circadian rhythm (CR), support their physiological resilience and enhance their capacity to heal. The recent completion of the RESTORE clinical trial (HL086622, PI [name]) provides evidence that critically ill children can be safely managed in a more awake state. Pilot work on PICU Up! (PI: [name]), an intervention promoting early progressive exercise and mobility in critically ill children, supports its safety and feasibility. We believe that more awake, responsive and active children who receive CR-restoring interventions may derive benefit. Our team, with expertise in pediatric critical care nursing, medicine, sleep, and pharmacology intends to shift the current PICU paradigm from potentially toxic to healing for the most vulnerable of patients. It is hypothesized that patients managed per **RESTORE resilience** will experience a more restorative circadian rhythm evidenced by an improved temporal sleep-wake pattern than patients receiving usual care. The overall aim of this study is to pilot test an individualized bundle of clinical care, RESTORE resilience (R2), in pediatric patients on mechanical ventilation for acute respiratory failure.

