2.2 Secondary Objectives (if applicable)

- Salivary melatonin levels on PICU day two and five
- Nighttime EEG slow-wave activity during endotracheal intubation with EMG and EOG
- R2 feasibility, adherence, system barriers
- Levels of patient comfort: PICU days free of pain, agitation, delirium, iatrogenic withdrawal
- PICU exposure to sedative medications (total dose and length of exposure)
- Time to physiological stability (time on vasoactive medication, duration of mechanical ventilation, PICU and hospital length of stay)
- Parent perception of being well-cared-for

3 Investigational Plan

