3.1 General Design

The study design is a two-phase prospective cohort study. Consecutive subjects will be enrolled into the Baseline Phase and then the Intervention Phase in two separate PICUs: Children's Hospital of Philadelphia and Johns Hopkins Children's Center.

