3.2 Allocation to Interventional Group [if applicable]

Following the baseline phase, all subjects will be enrolled in the intervention phase. No randomization or subject group allocation will occur.

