3.4 Study Endpoints

3.4.1 Primary Study Endpoint

The study endpoint will be PICU discharge or PICU day 28, whichever occurs first.

4 Study Population and Duration of Participation

The target population for this study is pediatric patients admitted to the PICU between the ages of 6 months and 18 years who are intubated and mechanically ventilated for acute airways or parenchymal disease, and are expected to be intubated for more than 24 hours.

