5.2.1 Data Collection and Follow-up for Withdrawn Subjects

Subjects who withdraw consent to participate in the study will be seen for one final study visit. During this visit they will be asked for permission to assess their survival status via medical records.

6 Statistical Plan

The study design will allow multiple comparisons; specifically baseline to intervention group and cross-unit comparisons. The specific aim of the study is to pilot test **RESTORE resilience**, an individualized chronotherapeutic bundle, in pediatric patients supported on mechanical ventilation for acute respiratory failure in the PICU. The study design is a two-phase prospective cohort study. Subjects will be consecutively enrolled into the Baseline Phase and then into the Intervention Phase in two separate PICUs. Each unit will enroll 10 baseline subjects followed by 20 intervention subjects (total: 20 baseline subjects and 40 intervention subjects). Outcome variables are designed to be as objective as possible since it is not possible to blind the assessor to treatment phase.

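### The primary comparison of two sequential, non-randomised phases is unadjusted, although the protocol itself ties age and severity to the outcome; the adjusted estimate is planned only outside the primary analysis

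*Combined protocol and SAP*

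**What the plan says.** **Design.** Section 3.1: "Consecutive subjects will be enrolled into the Baseline Phase and then the Intervention Phase in two separate PICUs". Section 3.2: "No randomization or subject group allocation will occur". Section 6 gives the numbers: 10 then 20 children per unit, so 20 baseline and 40 intervention in total.

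**Primary analysis.** Study Summary, Statistical Methodology: "Our primary analysis will compare the circadian activity ratio post-extubation between Baseline Phase and Intervention Phase patients using t-tests or Wilcoxon rank-sum tests". No covariate is attached to this test. Section 6.3.2 defines the outcome (the average ratio of daytime to 24-hour activity after extubation) and names no test, model or covariate.

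**Adjusted analyses.** The same Study Summary entry continues: "Secondary analyses will use linear regression to control for variables that could be associated with outcomes, such as patient severity or age group". It also plans regression for main effects and effect modification by gender, race/ethnicity and center. The severity measure and the age-group boundaries are not named. The timeline table in section 5.1 shows that demographics and a Day 1 PRISM III score are collected.

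**Confounding.** Section 6.3, the section on bias and confounding, relies on two things: approaching all eligible children consecutively, and using objective endpoints. Section 6.3.1 only describes baseline characteristics.

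**Purpose.** Section 6.1 says the study is not powered for effect and that feasibility is the interest. Section 6.2 calls it exploratory and says its estimates will feed power calculations for a later trial.

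**The concern.** An unadjusted two-sample test suits groups that differ only by chance. Here the groups are separated by calendar period, and nothing in the design makes their case mix alike.

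The protocol gives the reason why this matters. Section 1.1 says that circadian rhythm may be lost as acuity rises, and that sleep recommendations in children follow age and neurological maturation. Eligible ages run from 6 months to under 18 years. Age and severity are therefore plausible predictors of the ratio on the plan's own account, and both are recorded.

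The two safeguards in section 6.3 do not reach this problem. Consecutive approach limits selection within a period, and objective endpoints limit assessor bias. Neither corrects a shift in age or severity between periods. Dividing by each child's total activity, as section 6.3.2 does, removes differences in amplitude. It does not remove an effect of age or illness on the split between day and night.

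At stake is the phase difference that the next trial's planners would naturally take from this pilot. A case-mix shift could move it in either direction, and the unadjusted confidence interval would not show it.

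**Working it through.** The plan has no SD, standard error or power figure to reproduce. The enrolment arithmetic is consistent: 2 × (10 + 20) = 20 + 40 = 60.

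**Inputs from the documents**
- Group sizes 20 and 40 (section 6).
- Anticipated fall in night activity from 50% to 30% of the total (section 6.2). The ratio then rises from 0.50 to 0.70, a difference of 0.20.

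**Assumed inputs (not in the documents)**
- SD of the ratio 0.15, with 0.10 to 0.20 as a range.
- Gap between phases in a covariate: 0.3 to 0.5 covariate SD.
- Correlation r of that covariate with the ratio: 0.3 to 0.5.

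**Step 1: sampling error of the unadjusted difference.** SE = SD × √(1/20 + 1/40) = 0.15 × 0.274 = 0.041. The 95% half-width with 58 df is 2.002 × 0.0411 = 0.082.

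**Step 2: bias from one unadjusted covariate.** Bias = gap × r × SD.

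| Gap (SD) | r | Bias at SD 0.15 | Bias / SE | Coverage of the unadjusted 95% CI |
|---|---|---|---|---|
| 0.3 | 0.3 | 0.0135 | 0.33 | 93.8% |
| 0.3 | 0.5 | 0.0225 | 0.55 | 91.6% |
| 0.5 | 0.5 | 0.0375 | 0.91 | 85.4% |

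Coverage is from the noncentral t distribution with 58 df. The ratio of bias to SE does not depend on the assumed SD. In ratio units, the low end at SD 0.10 is 0.3 × 0.3 × 0.10 = 0.009, and the high end at SD 0.20 is 0.5 × 0.5 × 0.20 = 0.050.

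**Step 3: against the anticipated effect.** At SD 0.15: 0.0135 / 0.20 = 7% and 0.0375 / 0.20 = 19%.

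**Step 4: what adjustment costs.** Residual df are 60 − 2 = 58 without adjustment. Site and PRISM III take one each. Age takes one (a single term) to three (four age groups). That leaves 55 to 53. Approximate ratio of adjusted to unadjusted SE = √[(1 − R²) × VIF × 58 / residual df], where R² is the share of outcome variance explained by the covariates. For a gap d in one covariate, VIF = 1 + (20/60)(40/60)d².
- Covariates not prognostic, no gap: √(58/55) = 1.03 to √(58/53) = 1.05.
- Covariates not prognostic, one gap of 0.5 SD (VIF 1.056): √(1.056 × 58/55) = 1.06 to √(1.056 × 58/53) = 1.07.
- R² = 0.25, no gap, 3 df: √(0.75 × 58/55) = 0.89.

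Adjustment therefore costs a few percent of precision at worst in these settings, and gains some if the covariates are prognostic.

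**The case against.** **Adjustment is already planned.** This is true. A reader might infer from the primary test that age, severity and center are ignored; the Study Summary shows that they are not. What stands is narrower: the adjusted estimate is not the headline, its covariates are given as examples, and PRISM III is not named as the severity measure.

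**The label matters little in a pilot.** Sections 6.1 and 6.2 disclaim power and call the work exploratory, and both estimates would be available to whoever plans the next trial. This limits the weight of the point. It does not remove it, because the stated use of the estimates is planning, and low precision is no reason to leave measured confounding in the lead figure.

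**The bias is assumed and smaller than the noise.** This also stands. Nothing in the documents shows a case-mix gap, eligibility criteria are the same in both phases, and every illustrated bias is below one SE and inside the half-width of 0.082.

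**The planned age grouping may be adequate.** A reader might infer that age has no planned form. In fact age group is a categorical form, and only its boundaries are missing. In a simulation with illustrative groupings (such as cuts at 2 and 6 years, age gap 0.5 SD, r 0.5, SD 0.15), grouping left a bias of at most about 0.006 across four shapes of age effect. Similar assumptions gave 0.007 to 0.031 without adjustment. Pre-specified groups are therefore acceptable.

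**Adjustment cannot repair a before-after design.** This is correct. Phase and calendar time coincide within each site, so time trends and unmeasured differences remain under either analysis.

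**Conclusion.** The point holds as a matter of which estimate leads. The primary comparison of two sequential phases leaves out two variables that the protocol itself links to circadian or sleep pattern, and section 6.3 offers nothing against a difference in them between periods. Under the stated assumptions about SD, gap and correlation, the bias is about 0.014 to 0.038, or 0.33 to 0.91 of an SE of 0.041. With no gap, or with covariates unrelated to the ratio, it is zero. The change is worth making because it is cheap, but the benefit is modest: a less confounded planning estimate.

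Three stronger readings are not supported:
- A false confirmatory claim: the study makes no such claim.
- Selective enrolment: the Study Summary has "A prospective cohort study with a convenience sample of patients admitted to the PICU at two study sites" where sections 3.1 and 6.3 say consecutive. That is a wording inconsistency and shows no selection.
- Distortion from unequal averaging windows: section 3.4.1 says "The study endpoint will be PICU discharge or PICU day 28, whichever occurs first", but this marks the end of participation. Section 6.3.2 says only that the average is taken after extubation, so the window is an inference, and nothing in the documents shows that it differs between phases.

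**What to change.** 1. In the Statistical Methodology entry and section 6.3.2, define the primary estimate as the phase difference in the circadian activity ratio, with 95% CI, from a linear model with phase, site, age and Day 1 PRISM III.
2. Before the data are analysed, fix the coding of age (named age groups, or another pre-specified flexible form) and of PRISM III.
3. Report the unadjusted t-test or Wilcoxon comparison alongside as supportive.
4. State in section 6.3 that calendar-time and unmeasured confounding remain after adjustment.

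**Cost.** This is a change of wording only, since demographics and PRISM III are already collected. The model uses 3 to 5 residual df, and the SE is a few percent larger if the covariates turn out not to be prognostic. A rule for missing PRISM III has to be added. Site is balanced 1:2 by design if enrolment goes to plan, so including it costs one df and mainly makes the model reflect how children were enrolled.

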The first step in this program of research is to pilot-test **RESTORE resilience (R2)**, a 7-item individualized bundle that we hypothesize will restore CR in critically ill children using a pre-posttest design. Two separate PICUs will each enroll 10 baseline subjects followed by 20 intervention subjects, 6 months to 18 years of age, who are intubated and mechanically ventilated for acute respiratory failure. Specifically, as soon as possible after PICU admission, parents will be interviewed to create an individualized chronotherapeutic bundle to include (1) focused effort to replicate the child's pre-hospitalization daily routine (bedtime/wake time, bedtime/arousal routine, nap time, feeding schedule, active periods), (2) cycled day-night lighting and modulation of sound to match the child's routine, (3) minimal yet effective sedation using a nurse-implemented goal-directed sedation plan (RESTORE), (4) night fasting with bolus enteral daytime feedings, (5) early, developmentally-appropriate, progressive exercise and mobility (PICU Up!), (6) continuity in nursing care, and (7) parent diaries. The overall objective of this study is to pilot-test an intervention that can be implemented in any PICU that will improve sleep-wake patterns with restoration/maintenance of circadian rhythms in critically ill children with acute respiratory failure. Results of this pilot study will be used to inform the design of an adequately powered multicenter randomized trial of R2.

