6.2 Statistical Methods

For purposes of this pilot study, we assume that subjects managed per R2 will exhibit maintain circadian rhythmicity and demonstrate an improved sleep-wake pattern, as evidenced by increased circadian activity ratio (daytime activity/total 24-hr activity) post-extubation, compared to those managed per usual care. Preliminary data from current studies in the PICU suggest that 50% of activity occurs during the nighttime hours in the PICU. We anticipate that the R2 intervention will result in a decrease in nighttime activity to 30% of total activity. **This pilot study is exploratory to determine preliminary estimates in order to develop power calculations for a future trial.**

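### The primary two-sample test ignores site, and its standard error covers child-to-child variation only, so its precision holds for these two units and periods and could be too optimistic beyond them

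*Combined protocol and SAP*

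**What the plan says.** The Study Summary, under Statistical Methodology, sets the primary analysis: "Our primary analysis will compare the circadian activity ratio post-extubation between Baseline Phase and Intervention Phase patients using t-tests or Wilcoxon rank-sum tests". Section 6.3.2 defines the circadian activity ratio but adds no model, stratification or interval.

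On design, Section 3.1 says "Consecutive subjects will be enrolled into the Baseline Phase and then the Intervention Phase in two separate PICUs", Section 3.2 says "No randomization or subject group allocation will occur", and Section 6 says "Each unit will enroll 10 baseline subjects followed by 20 intervention subjects (total: 20 baseline subjects and 40 intervention subjects".

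Site is not forgotten altogether. The Statistical Methodology text expects no difference by centre, but plans regressions for centre main effects and for effect modification by centre. Section 6 also announces cross-unit comparisons. Both sit outside the primary test. No clustering, period or ICC term appears anywhere.

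On purpose, Section 6.1 says the study is not powered for effect and that the interest is feasibility. Section 6.2 calls it exploratory, intended to "determine preliminary estimates in order to develop power calculations for a future trial". Section 2 describes that trial as an "adequately powered multicenter randomized trial of R2".

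**The concern.** Children treated in one unit during one phase share staff, routines and part of their environment. Phase switches once in each unit, so there are four unit-by-period cells and one before-after difference per unit. A two-sample test on 20 and 40 children treats all 60 as independent. If unit conditions drift between periods for reasons other than R2, that drift enters the phase difference but not its SE.

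The test also sets aside the site structure that the quotas create. At stake is how firmly the pilot's main contrast can be read, and whether someone planning a multicentre trial can see what its uncertainty covers.

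A time change common to both units is a separate matter. It would bias the estimate, and this point does not concern it.

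**Working it through.** The plan gives no power calculation, alpha, SD or ICC, so there is no stated figure to reproduce beyond the count: 2 × (10 + 20) = 20 + 40 = 60, which agrees. Results below are in SD units with total variance 1. A two-sided 5% level and all ICCs are assumptions.

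**1. Independent children.** Variance of the phase difference = 1/20 + 1/40 = 0.075; SE = √0.075 = 0.274. The 95% half-width is 0.548 (t, 58 df).

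**2. With a unit-by-period ICC ρ.** A cell mean has variance ρ + (1 − ρ)/n, with n = 10 or 20. Averaging the two site differences gives

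Var = ¼ × 2 × [2ρ + (1 − ρ)(1/10 + 1/20)] = ρ + 0.075(1 − ρ).

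Large-sample error of a nominal 5% test = 2[1 − Φ(1.96/ratio)], where ratio = √(Var/0.075). The last two columns are from 40,000 simulated trials per setting, using the pooled t-test with no stable site difference. The rank-sum test was not simulated.

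| Assumed ρ | Var | SE | Ratio | Error, formula | Error, simulated | Coverage of 95% CI |
|---|---|---|---|---|---|---|
| 0 | 0.0750 | 0.274 | 1.00 | 5.0% | 5.1% | 94.9% |
| 0.01 | 0.0843 | 0.290 | 1.06 | 6.4% | 6.6% | 93.4% |
| 0.02 | 0.0935 | 0.306 | 1.12 | 7.9% | 7.9% | 92.1% |
| 0.05 | 0.1213 | 0.348 | 1.27 | 12.3% | 12.5% | 87.5% |
| 0.10 | 0.1675 | 0.409 | 1.49 | 19.0% | 19.2% | 80.8% |

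**3. A stable site difference.** With the same 10:20 split at both sites, it cancels from the phase difference but stays in the pooled test's residual variance. With ρ = 0, simulated error is 4.7% at a unit ICC of 0.05 and 4.3% at 0.10, so the pooled test is slightly conservative. A phase + site model gives 5.0% and 4.9%.

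If usable post-extubation data depart from 10:20, the cancellation fails. The pooled contrast is then shifted by the site difference times the gap in site mix between phases.

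**4. Does adding site cure step 2?** No. With phase + site, simulated error is 6.6%, 8.0%, 12.7% and 19.8% at ρ = 0.01, 0.02, 0.05 and 0.10.

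**5. Can the planned effect-modification analysis show that the sites agree?** The site-by-phase interaction has SE = √[2(1/10 + 1/20)] = √0.30 = 0.548 SD. For 80% power it must be about (1.96 + 0.84) × 0.548 = 1.53 SD. For scale, Section 6.2 says "Preliminary data from current studies in the PICU suggest that 50% of activity occurs during the nighttime hours in the PICU" and anticipates 30% under R2, a shift of 0.20. At an assumed SD of 0.20, 1.53 SD is 0.31, more than the whole anticipated effect.

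**6. A unit-level analysis.** Two site differences leave 1 df, with a critical t of 12.7. No useful interval that includes unit-by-period variation can come from two units.

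**The case against.** The strongest reply is that this is a two-site, exploratory pilot that disclaims power. Inference conditional on the two PICUs is legitimate, and no interval or alpha is stated, so no figure in the plan is wrong. That stands. The plan nevertheless names a hypothesis test as its primary analysis and offers its estimates for planning, so a reader needs to know what the uncertainty covers.

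Shared conditions can also be overstated. Light and noise are monitored in the patient's room. In the intervention phase, light, sound and feeding follow each child's own routine, and children are enrolled over time (Sections 3.1 and 5). This argues for a modest ICC, possibly near zero, but does not establish zero.

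Three stronger readings are tempting, and the documents do not support them:

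- *The error bars are too narrow, full stop.* This depends on an ICC that the documents do not give; at zero there is no excess.
- *Disagreement between the two units would pass unnoticed.* Effect modification by centre and cross-unit comparisons are planned. Their weakness is imprecision, not absence.
- *The future trial will be sized on this pooled SE.* No section says so. The planned descriptive SDs are the natural input. The unit of randomization is not stated, and if children are randomized within units, shared unit-period effects largely cancel.

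**Conclusion.** The point holds in conditional form. The primary test ignores site, and its SE describes child-to-child variation only. For these two units in these two periods, that is a fair description of precision, and slightly cautious if the sites differ stably. For any wider reading, the true SE is larger by 0% to 49%, and the error of a nominal 5% test is about 5% to 19%, as the assumed unit-by-period ICC runs from 0 to 0.10. The upper end rests on an assumed value that nothing in the documents fixes.

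The planned centre analyses do not alter the primary SE, and a null interaction would not show agreement. It would be wrong to conclude that the design yields a mis-sized future trial, or that a different test would repair it.

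**What to change.** 1. In the Statistical Methodology text and Section 6.3.2, make the primary estimate the site-stratified phase difference, or the phase coefficient from a phase + site model, with a CI. If a rank method is needed, use a site-stratified one.
2. Beside it, report each site's 10 versus 20 difference with its CI. Each has SE √(1/10 + 1/20) = 0.387 within-site SD, so these are for display and not a test of agreement.
3. In Section 6.2, state that the interval is conditional on these two units and periods, and that two units cannot estimate unit-by-period variation.
4. For future power calculations, carry forward the within-site SD. If units or periods are to be randomized, add external unit-by-period ICCs over a stated range.

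The cost is some wording, one extra table and a narrower stated conclusion; no new data are needed. The gain is error bars corrected for stable site differences, protection if usable data depart from 10:20, and a clear limit on inference. Unit-by-period error remains.
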